| 4 | 0.8 | Day 1 |
| 5 | 1.5 | Day 1 |
| 6 | 3 | Day 1 |
| 7 | 6 | Day 1 |
| 8 | 12 | Day 1 |
| 9 | 25 | Day 1 |

Table 6: Initial Dose Escalation

If symptoms, including intolerable localized itching or any systemic reaction, occur, the dose escalation will be stopped and the participant will be sent home on daily doses of the highest dose tolerated (must be at least 3 mg with a maximum of 25 mg). Mild symptoms during escalation can be treated with a single dose of antihistamine with continued milk dosing.

D. Dose Build-Up:

Further dose increases at approximately 50% increments will occur under observation approximately every 2 weeks as listed below in Table 7, with daily home dosing between each observed dose increase. The interval history and dosing log will be reviewed. A gastrointestinal assessment will be done at least once a month. At each visit, alimited physical exam and peak flow testing will be conducted. Urine pregnancy testing will be done every month if indicated. If the participant did not reach 25 mg on the initial dose escalation, they will follow the dose escalation day schedule approximately every 2 weeks until they reach 25mg. At these visits, subjects will demonstrate understanding of preparation and administration of the OIT doses and be observed for reactions for a minimum of 60 minutes. The final dose tolerated will be taken at home for the next 2 weeks (range of 10-21 days). The tolerated protein dose will be dispensed in portion cups. The powder will be packaged into cups by [name] manufacturing facility at the University of North Carolina and shipped to Johns Hopkins Research Pharmacy. Drug dispensing will be performed by Johns Hopkins research pharmacy. The subject's guardian will be given detailed instructions on how to add the powder to a muffin or cupcake for their daily dosing, and bake at 350°F/180°C (at least) for at least 30 minutes.

If the dose is not tolerated, the subject will resume the highest previously tolerated dose until their next visit. The minimum accepted dose for maintenance daily OIT dosing is 750 mg. If the patient does not tolerate three consecutive escalation attempts, but has attained a dose of 750 mg, this dose will become the maintenance daily home dose until the year 1 OFC (DBPCFC #2). If the patient does not tolerate three consecutive escalation attempts and 750 mg has not been obtained, then the study treatment will be discontinued. In addition, OIT will be discontinued for subjects

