At the end of study year 2 (week 106), study participants will undergo DBPCFC #3 to baked milk with dosing as listed above in Table 4. Participants will be asked to fill out a gastrointestinal assessment and quality of life questionnaire prior to DBPCFC #3. A limited physical exam, urine pregnancy test (if indicated) and peak flow rate will be conducted. Blood will be collected and skin testing will be repeated. If the exam is normal, urine pregnancy test is negative, and PFR \geq 80% of normal, the study participants will undergo an oral food challenge with a cumulative dose of 4044 mg of either baked milk or placebo in a blinded manner. Participants will receive doses every 15 minutes and will be monitored for symptoms of allergic reaction. The second half of the DBPCFC will occur within 21 days. If no symptoms occur during the first half of DBPCFC#3, then the second half of the challenge could occur on the same day at the discretion of the principal investigator.

5. Study Year 2 OFC to Unheated Milk (DBPCFC #4)

Within two weeks of the completion of DBPCFC #3, study participants who tolerated at least 2000 mg of baked milk during DBPCFC #3 will undergo DBPCFC#4 with a cumulative of 8030 mg of unheated milk powder or placebo in a blinded manner with dosing as listed in table 5. A limited physical exam, urine pregnancy and peak flow rate will be conducted. If the exam is normal, urine pregnancy test is negative, and PFR \geq 80% of normal, the study participants will undergo an oral food challenge to unheated milk powder or placebo. The second half of the DBPCFC will occur within 21 days. If no symptoms occur during the first half of DBPCFC#4, then the second half of the challenge could occur on the same day at the discretion of the principal investigator.

H. Follow-up Period:

- 1. Subjects who discontinue study treatment before the end of the study will complete an Early Discontinuation Visit 1-2 weeks after their last dose of study treatment. During that visit, they will have a physical exam and urine pregnancy test (if applicable). Daily diaries and interval history will be reviewed. Subjects who complete DBPCFC#2 and then leave the study early will be asked to sign a consent to participate in follow-up (as detailed below in #4) if they have been given instructions to introduce milk at home.

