Those completing the treatment course will be followed as described above; those that withdraw or do not complete the course of treatment will have a follow-up visit within 1-2 weeks after stopping the study. The study termination visit will include: 1) A final physical exam, 2) a pregnancy test for female participants of child bearing age, and 3) a review of the interval history and daily diary.

If subjects complete DBPCFC#2 and then leave the study early, we will ask them to sign a separate consent to participate study in study follow-up if they have been given instructions to introduce milk at home.

All participants who complete treatment will have telephone follow-up quarterly for 1 year and then a clinic visit 6, 12, and 24 months post-study completion. This follow-up visit will include a limited physical exam, dietary history, food reaction history, skin prick tests, blood collection, gastrointestinal symptom questionnaire, and a quality of life questionnaire.

5. Inclusion/Exclusion Criteria

Patients who meet *all* of the following criteria are eligible for enrollment as study participants, including participants who:

- Are age 3-18 years, either sex, any ethnicity or race
- Provide signed informed consent by parent or legal guardian and informed assent if applicable
- Have a history of symptomatic reactivity to cow's milk (i.e. eczema, urticarial, upper or lower respiratory symptoms, GI disturbances, rash, oral symptoms)
- Have a skin prick test positive to milk (diameter of wheal 3 mm \ge negative control) and serum milk-specific IgE level >5 kU/L within the past 6-12 months
- Have a positive reaction to a cumulative dose of ≤444 mg of baked milk protein in the initial qualifying DBPCFC.
- Use an effective method of contraception by females of childbearing potential to prevent pregnancy and agree to continue to practice an acceptable method of contraception for the duration of their participation in the study.
- Have self-injectable epinephrine available at all times

Patients who meet *any* of these criteria are not eligible for enrollment as study participants, including participants who:

- Have a history of severe anaphylaxis resulting in hypotension, neurological compromise, or mechanical ventilation
- Have a history of intubation related to asthma
- Tolerate more than 444 mg of baked milk protein at the initial qualifying DBPCFC.
- Allergy to placebo ingredients OR reacts to any dose of placebo during the qualifying OFC.

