The study treatment is non-fat cow's milk powder or placebo ingested in a baked form. The non-fat cow's milk powder will be provided by the University of North Carolina (UNC). It is manufactured by The Milky Whey, Inc & TMW International. It will be refrigerated at the site at 2 through 8°C until provided to the participants. Detailed instructions will be provided regarding how the baking should be performed.

The doses chosen are based on prior milk OIT studies, which have all used unheated milk. We anticipate similar efficacy with greater safety using this approach.

b. Justification and safety information if FDA approved drugs will be administered for nonFDA approved indications or if doses or routes of administration or participant populations are changed.

Aside from the skin testing extracts, this study will not use any drugs, but rather foods commonly available in households, prepared using a standard oven. Most milk OIT studies to date have used unheated milk at maintenance doses ranging from 500- 4000 mg. As described in the background section, these have shown high rates of adverse reactions, ranging from mild, local symptoms, such as oral itching, to systemic allergic reactions.

Baking milk has been shown to modify the allergen and make it less allergenic and therefore less likely to induce adverse reactions. It has been shown that 50-75% of children with

CMA tolerate baked milk at full servings, such as a cupcake or muffin, and many are already incorporating these foods into their diet at home.¹³ However, the remaining 25-50% of children with CMA are not able to tolerate baked milk at standard doses. Our dosing regimen will start with extremely small doses of baked milk protein and gradual escalation.

We believe that the chemistry and manufacturing of the non-fat milk powder and Tapioca Flour does not present signals of potential human risk, beyond the inherent risk associated with the investigational treatment protocol. This milk powder has been approved by the Food & Drug administration for use in other clinical trials (IND: 77,468) and in our study (IND: 17114).

c. Justification and safety information if non-FDA approved drugs without an IND will be administered.

N/A

7. Study Statistics

a. Primary outcome variable.

The primary objective of this trial is to study the safety of baked milk OIT, defined as the incidence of adverse events on baked milk OIT compared to adverse events on placebo.

b. Secondary outcome variables.

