As mentioned previously, there has only been 1 prior study using baked milk OIT. Goldberg et al had a different primary outcome which was the goal of attaining a maintenance BM dose of 1.3g/day.²⁸ Only 21% reached that goal but as mentioned above, the study protocol was different than our study protocol.

Based on these prior studies, we would expect that at most 10% of subjects in the placebo arm and at least 60% of subjects in the treatment arm would tolerate 2 grams of unheated milk at the 1 year OFC. To achieve an alpha of 0.05 and a power of 0.8, 14 subjects are needed in each group. 15 participants per group would allow for a 7% drop out rate.

Statistical plan:

We will display summary statistics for each variable to keep track of missing data, and to be alerted to suspicious patterns in the data and outliers. We will initially focus on the primary aim of the study. We will examine adverse event endpoints to estimate 1) the risk associated with OIT and 2) compare the risks of OIT between the risks of adverse reactions in the placebo group. We will tabulate the total number of serious adverse events (SAE) for the active treatment study population and construct a 95% confidence interval for this total number of adverse events. We will also calculate the proportion of subjects who experienced an SAE along with the 95% CI. We will calculate the proportion of subjects who experienced an SAE and construct the 95% CI. We will compare the proportion of doses resulting in an SAE between groups using Fisher's exact test. We will compare the number of adverse events between groups using the Kruskall-Wallis test if the variances between the groups are similar.

In addition to efficacy endpoints, we will tabulate data and calculate the proportion of subjects who achieved a clinical response and construct 95% confidence intervals. We will do this for each time point being evaluated so that we have estimates of clinical response rates after completion of 1 year of OIT, after 2 years of OIT, and after 1 year of placebo.

We will also compare clinical response rates between the active treatment and placebo groups at the year 1 and year 2 OFCs. We will tabulate the clinical response rates by group for each time point and use a t-test for difference in proportions to test for statistical significances in response rates between groups.

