Within the context of this study, blood draws, allergy skin prick tests, dose increases and oral food allergy challenge tests will be observed and recorded. Adverse events (AEs) that are temporally related to these procedures or to home dosing with the study medications (during 3 days following the procedure) will be reportable adverse events. Anticipated local reactions to prick skin tests and oral food challenges reactions occurring during the challenge procedure will not be additionally reported on an adverse event form unless the reaction results in a serious adverse event. In that case it will be reported both on the reaction form and on a serious adverse event form.

The following events would be considered expected events for the procedures being performed:

- Blood draw: nausea and vomiting, local infection, and fainting
- Prick skin test: Pruritus, transient hive, systemic allergic reaction
- Oral food challenges and dosing with study medications: allergic reactions related to the skin (hives, pruritus, eczema flare), the respiratory tract (nasal congestion, rhinorrhea, fits of sneezing, difficulty breathing, asthma), and the GI tract (oropharyngeal pruritus and edema, nausea, vomiting and diarrhea).

All "unanticipated" adverse events related to the experimental procedures will be reported to the DSMB in an expedited manner if they are Grade 2 and above in severity. All "anticipated" adverse events related to the experimental procedures will also be reported in an expedited manner if they are Grade 2 and above in severity. Subject deaths are reportable within 24 hours. The investigator will continue to follow or obtain documentation of the resolution course of such an event. A copy of the annual report of adverse events will be reported to the IRB.

iv. Data and Safety Monitoring:

A Data Safety Monitoring Board will be convened for overview of this study. The Principal Investigator and Co-Investigators are responsible for collecting and recoding all clinical data. As these results are collected, all toxicities and adverse events will be identified and reported to the PI. Adverse events will be reported as described above. The Principal Investigator will determine the relationship of the event to the study intervention and decide the course of action for the study participant.

Yearly reports will be made to the DSMB and proper Institutional Committees, as required. All adverse events will be kept in a computerized file by numerical identifier.

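### The only planned between-group test of all adverse events, the primary endpoint, runs only if variances are 'similar', a condition that is undefined, not needed for validity and likely to fail when OIT raises event numbers

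*Combined protocol and SAP*

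**What the plan says.** Sections 2 and 7a define the primary endpoint as "the incidence of adverse events on baked milk OIT compared to adverse events on placebo". Under the primary aim, the statistical plan in Section 7c undertakes without condition to "compare the risks of OIT between the risks of adverse reactions in the placebo group". It then names two between-group safety tests:

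- SAEs only, per dose: "We will compare the proportion of doses resulting in an SAE between groups using" Fisher's exact test.
- All adverse events: "We will compare the number of adverse events between groups using the Kruskall-Wallis test if the variances between the groups are similar".

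The t-tests in Section 7c concern clinical response and tolerated dose. No section gives a criterion for similar variances, a variance test, or an alternative if the condition fails.

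Three other provisions affect how many events a child can contribute. Dosing can end because of reactions, for example: "If the patient does not tolerate three consecutive escalation attempts and 750 mg has not been obtained, then the study treatment will be discontinued" (Section 4, D; also the week-44 rule there and the list in Section 4.e). Reportable events are those close in time to a study procedure "or to home dosing with the study medications (during 3 days following the procedure) will be reportable adverse events" (Section 8.c.iii). A child who stops early "will complete an Early Discontinuation Visit 1-2 weeks after their last dose of study treatment" (Section 4, H; Section 4.f says much the same).

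**The concern.** The variances of adverse-event counts are known only once the outcome data exist. The primary comparison is therefore settled after those data are seen, under a rule that two competent analysts could apply differently. The condition is also not neutral. Event counts spread out as their mean rises, so the rule tends to withdraw the test in the situation it is meant to detect. Read literally, the plan then has no test of all adverse events. In practice someone would choose another test with the arm data in view.

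A lesser issue is that the test uses the number of events with no dose denominator, although the SAE comparison has one. If the most reactive children on OIT stop early, their counts are cut short.

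**Working it through.** **The plan's own figure.** The only sample size is for efficacy: 10% versus 60%, alpha 0.05, power 0.80. With pooled variance and two-sided alpha, n = [1.96·√(2·0.35·0.65) + 0.842·√(0.1·0.9 + 0.6·0.4)]² / 0.5² = (1.322 + 0.483)² / 0.25 = 13.04, so 14 per group as stated, and 15 with dropout. Nothing is sized for adverse events, and no adverse-event rates are given for this trial. The rates below are therefore assumptions.

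**Does the test need the condition?** With two groups, Kruskal-Wallis is the Wilcoxon rank-sum test. If treatment has no effect, both arms have the same distribution and the ranks are exchangeable, whatever its shape. In simulation under equal rates the unconditional test rejects in 0.044-0.051 of trials. Similar spread matters only for reading the result as a shift in location.

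**Why the condition fails when OIT causes events.** Assume 365 blinded doses and child-specific rates that vary as a gamma distribution with shape k (k = 1 wide, k = 4 narrow). A count with mean m then has variance m + m²/k. At an assumed 5% of doses on placebo, m = 18.25; a threefold excess gives m = 54.75.

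- k = 1: (54.75 + 2997.6) / (18.25 + 333.1) = 3052 / 351 = 8.7.
- k = 4: (54.75 + 749.4) / (18.25 + 83.3) = 804 / 101.5 = 7.9.

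A threefold excess in events thus gives about an eightfold difference in variance.

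**How often it fails.** The table shows 15 per arm, placebo 2% or 5% per dose, both values of k, no stopping, and 10,000 trials per setting. The two criteria are stand-ins for 'similar'; neither is in the documents.

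| True excess | Levene p < 0.05 | Variance ratio above 4 |
|---|---|---|
| none | 4-5% | 4-15% |
| twofold | 26-39% | 39-49% |
| threefold | 55-77% | 78-85% |
| fivefold | 84-97% | 96-99% |

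**What this costs.** These are frequencies of discretion, not of missed harm. Suppose a Welch test replaces the rank test whenever Levene fails. Detection at 2-, 3- and 5-fold is then 0.37-0.39, 0.73-0.75 and 0.95-0.96 (wide), against 0.32-0.34, 0.66-0.68 and 0.92-0.93 for the unconditional rank test. With narrow variation the two are also close (0.85-0.90 against 0.83-0.88 at twofold). At a two- to threefold excess, the rank and Welch tests disagree on significance in 11-14% of trials (wide) or 0.1-6% (narrow). Taking the better of the two under equal rates gives an error of 0.055-0.065.

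**Raw counts versus counts per dose.** Assume 15% versus 5% per dose, wide variation, and the 3 most reactive of 15 OIT children stopping. Power of the rank test is:

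| When they stop | Counts | Per-dose rates |
|---|---|---|
| spread over doses 42-308 | 0.58 | 0.67 |
| all at dose 60 | 0.41 | 0.66 |
| week 44 | 0.66 | 0.67 |

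If true rates are equal and those 3 OIT children stop at dose 60 with no placebo stops, counts significantly favour OIT in about 18-28% of trials, against about 3% for rates. Three of 15 is 20%, the top of the 10-20% reaction-related dropout cited in Section 8.a.i. The one earlier baked milk study had 8 of 14 (57%) not completing because of reactions (Section 3).

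**The case against.** The condition has a rationale: with similar spread, a rank test can be read as a location shift. That stands, but it governs interpretation. It is no reason to withhold the test, and it does not supply a fallback.

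A reader might infer that the trial could end with no primary safety comparison, or miss a large harm. The documents do not support that. The aim of comparing risks is unconditional, the per-dose SAE test has no such condition, and Section 7d has stopping rules for severe reactions. A reasonable substitute test would also keep detection. What is missing is a fixed test of all events.

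A reader might also infer that raw counts are an error because reactions end dosing. That goes too far. Under Section 4, D, a single dose that is not tolerated sends the child back to an earlier dose. Stopping follows severe or persistent reactions, repeated failed escalations below 750 mg, or missing 750 mg by week 44. Events per randomized child, with stopping as part of what happens, is a legitimate question. A per-dose rate answers a different one.

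Finally, every power figure depends on assumed rates and stop times. That also stands, and the figures are illustrative.

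**Conclusion.** The condition is wrong as written and should be removed. It is undefined, has no alternative, is unnecessary for validity, and tends to fail when OIT raises event numbers. The consequence is a primary comparison that is not fixed in advance. Inflation from choosing between two sensible tests is small (0.055-0.065 against 0.05), so this is a specification fault rather than a serious loss of safety information.

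The missing denominator supports a secondary analysis, not a charge of error. The loss from counts is about 9 points for three spread stops (0.67 - 0.58) and 25 points if all three stop early (0.66 - 0.41), at a threefold excess with wide variation. It is close to nil for week-44 stops.

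Confidence is high on the text. It is moderate on size, which rests on assumed event rates, between-child variation, stop times and a stand-in for 'similar'.

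**What to change.** Replace the conditional sentence in Section 7c with:

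> The number of adverse events per child during the blinded period will be compared between arms, in all randomized children who took at least one blinded dose, by a two-sided Wilcoxon rank-sum (Kruskal-Wallis) test, with no condition on variances.

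Add one prespecified supporting analysis: the same rank test on events per dose taken, with doses taken, time on dosing and stops for reactions shown by arm.

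If a negative-binomial rate ratio with a log(doses) offset is also reported, label it approximate. In checks its 95% interval covered 90-94%. With a true ratio of 3 and the three most reactive OIT children stopping, its median was 3.2-3.4 when event rates in the first 154 doses were twice the later rate.

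The per-dose rate has limits. It is unstable for children with few doses, it can be distorted if event rates change over the year, and in one set of simulations its error rose to 7-10% under heavy early stopping. That is why it should support the count comparison, not replace it.

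The cost is a wording change and minor programming. The daily diary and dosing log in Section 4, D already capture doses and events, so no new data or visits are needed.

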|-------------------------|------|--------------------------------------|-----------------|------|------------------------------------|-------------|---|
| Nariesty ²³ | 2009 | Open label (Follow up) | n=13 | 6-16 | 500 to 4,000 mg milk protein | 3-17 months | Ongoing milk intake demonstrated tolerance from 1000 to 16,000 mg (median 7000) with 33% tolerating 16,000 mg on OFC |
| Pajno ²⁴ | 2010 | Randomized, placebocontrolled | n=15 | 4-10 | 200 mL | 18 weeks | 67% tolerant to 200 mL cow's milk |
| Martorell ¹⁹ | 2011 | Randomized, placebocontrolled | n=30 | 2-3 | 200 mL | 1 year | 90% showing complete desensitization |
| Keet ¹⁸ | 2012 | Randomized, OIT vs SLIT | n=20 for OIT | 6-17 | 1000-2000 mg | 60 weeks | 70% of patients receiving OIT passed an 8g OFC. Only 40% passed OFC when treatment was discontinued for 6 weeks. |
| Wood ²⁷ | 2015 | Omalizumab DBPC, openlabel OIT | n= 57 | 7-32 | 3300 mg | 24 months | 80% desensitized to 10 g OFC, Sustained unresponsiveness in 42% after 8 week |

However, OIT studies to date have shown high rates of adverse reactions, ranging from mild, local symptoms, such as oral itching, to severe systemic symptoms, such as anaphylaxis.^{12,26} In 2011, Martorell et al conducted a 1 year milk OIT study in 2-3 year old children. While 90% were desensitized, 47% developed moderate reactions (rhinoconjunctivitis, wheezing, vomiting, urticaria) over the course of treatment.¹⁹ In 2012, we examined the safety and efficacy of OIT and SLIT (sublingual immunotherapy) for cow's milk allergy. The study reported reactions in 30% of doses with most confined to oral pruritus, but with more significant reactions with OIT compared to SLIT.¹⁸ In addition, 10-20% of subjects have dropped out of OIT trials due to adverse reactions, most commonly chronic abdominal pain.^{12,26}

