Many of the 25-50% of cow's milk allergic patients who do not tolerate heated milk have a very severe, persistent phenotype. These children have a high risk of reactions due to accidental exposures and a low likelihood of naturally outgrowing their allergy and therefore, would benefit greatly from a safe and effective form of treatment. Our hypothesis is that children with IgE mediated CMA who are reactive to baked milk can be desensitized to cow's milk protein via baked milk OIT, and that this approach will prove far safer than OIT using unheated milk. We propose to explore the efficacy and safety of baked milk OIT in a double-blind, placebo-controlled study in children with persistent CMA, focusing on the more allergic children who are 1) unable to tolerate baked milk even at small servings; 2) unlikely to naturally outgrow their milk allergy; and 3) more likely to have difficulty tolerating OIT with uncooked milk.

This approach has this far been attempted in one small study in Israel with 15 baked milk reactive patients.²⁸ The primary outcome was defined as attaining a maintenance baked milk dose of 1.3 grams per day without adverse reactions at 1 year of treatment. This study started with a baked milk dose of 25-120 mg. Only 3/14 (21%) patients tolerated the 1.3g goal dose. Eight did not complete the program because of IgE-mediated reactions and 3 did not complete it for other reasons.

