Unheated oral immunotherapy has shown a high rate of adverse reactions. In 2011, Martorell et al conducted a 1 year milk OIT study in 2-3 year old children. While 90% were desensitized, 47% developed moderate reactions (rhinoconjunctivitis, wheezing, vomiting, urticaria) over the course of treatment.¹⁹ In 2012, we examined the safety and efficacy of OIT and SLIT (sublingual immunotherapy) for cow's milk allergy. The study reported the reaction rate during the initial OIT escalation (36%), 1000 mg OIT escalation and maintenance (30%), and 2000 mg OIT escalation and maintenance (27%).¹⁸ The majority of symptoms were mild and localized to oral pruritus.¹⁸ During this study, antihistamines were used in 11% of doses during initial OIT escalation, 3.5% of doses in the 1000 mg escalation and maintenance, and 11% of doses in the 2000 mg OIT escalation and maintenance. A β -agonist was required in 1.5%, 2%, and 1.5% of doses in each respective group. Epinephrine was used for 4 OIT doses.¹⁸ In addition, 10-20% of subjects have dropped out of OIT trials due to adverse reactions, most commonly chronic abdominal pain.^{12,26}

We would view these risks as worst case scenario, since we expect far fewer adverse reaction with the heat modified milk proteins.

ii. Allergy Skin Testing

There is a risk of minor discomfort and itching and a transient hive. A localized wheal and flare will occur at the site of the histamine control. A similar reaction may occur at the site of milk extract. Fewer than 5 in 10,000 tests results in a systemic reaction (e.g. sneezing, runny nose, itchy eyes, or hives), and, even more rarely, systemic reactions that can be life-threatening.²⁹⁻³² There have been no systemic reactions in the principal investigator's experience with over 75,000 skin tests.

iii. Blood Collection

There is a risk of minor discomfort or bruising at the site of the blood draw. Some people may experience lightheadedness. Very rarely, an infection can develop at the site of the venipuncture.

iv. Spirometry and Peak Flow

The minor risk is of slight discomfort associated with forceful expiration and, occasionally, lightheadedness.

v. Oral food challenge

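### The only between-arm test of all adverse events uses raw counts with no exposure denominator, although reaction-driven stopping probably shortens exposure mainly on active treatment

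*Combined protocol and SAP*

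**What the plan says.** Section 7.a makes safety the primary outcome, "defined as the incidence of adverse events on baked milk OIT compared to adverse events on placebo". It gives no unit or denominator.

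Section 7.c names two between-group safety tests. For serious events, "We will compare the proportion of doses resulting in an SAE between groups", with Fisher's exact test. For all adverse events: "We will compare the number of adverse events between groups using the Kruskall-Wallis test if the variances between the groups are similar". The section also says that the risks in the two arms will be compared, but attaches no other test to that aim.

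Several rules end dosing early:

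- Section 4.D stops treatment after three consecutive failed increases below 750 mg, or if 750 mg is not reached by week 44.
- Section 4.e adds severe anaphylaxis, severe symptoms needing aggressive therapy, and ongoing severe gastrointestinal symptoms.

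Section 8.c.iii ties reportable events to procedures and home dosing, with a three-day window. Section 4.H gives early stoppers one visit one to two weeks after the last dose.

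**The concern.** A child whose dosing stops at week 11 has about a fifth of the observation time of a child who reaches the week-52 challenge, yet both enter the test as one count. If the children who stop are mostly on active treatment, and stop because they react, the arm with the higher event rate has its counts cut short. The comparison then leans towards making OIT look safer than it is per unit of treatment, on the primary outcome. The plan already uses an exposure denominator for serious events, so leaving it out for the wider comparison looks unintended.

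That stopping falls mainly on active treatment is an inference. The documents support it in three ways. Section 3 reports that "10-20% of subjects have dropped out of OIT trials due to adverse reactions". Children who react to placebo in the qualifying challenge are excluded (Section 5). The placebo group is expected to attend the full year-1 schedule (Section 4, study duration).

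There is a secondary loss. The 2012 OIT trial that the protocol uses as a safety reference is summarised per dose: "The study reported reactions in 30% of doses with most confined to oral pruritus". Counts per child cannot be set beside that figure, although Section 3 predicts that "this approach will prove far safer than OIT using unheated milk".

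**Working it through.** **The plan's own figure.** The plan gives no number for the adverse-event comparison. Its sample size concerns efficacy (10% against 60%, alpha 0.05, power 0.80) and reproduces with the two-sided pooled formula: [1.960·√(2·0.35·0.65) + 0.842·√(0.1·0.9 + 0.6·0.4)]² / 0.5² = 13.04, rounded up to 14. The allowance is stated as "15 participants per group would allow for a 7% drop out rate"; 1/15 = 6.7%. Neither figure bears on the safety test.

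**Inputs from the documents.** 15 per arm; one stopper of 15 (the plan's 7%) or three of 15 (20%, the top of the range cited from OIT trials); week 52 for the year-1 challenge; week 44 as the last stopping point in build-up.

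**Assumed inputs.** Rate ratio 2 among completers; all stops in the active arm; events spread evenly over 52 weeks; stopper rate m times that of active completers, with m = 1 or 3; stop week s = 11 or 44. With increases about every two weeks, three consecutive failures could occur by about week 6, so week 11 is possible under the rules.

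**Ratios.** With k stoppers:

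- count ratio = 2·[(15 − k) + k·m·s/52]/15
- full-exposure ratio = 2·[(15 − k) + k·m]/15

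Example, k = 3, m = 3, s = 11: 2·(12 + 9·11/52)/15 = 1.85, against 2·(12 + 9)/15 = 2.80.

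| Stoppers | Stop week | m | Count ratio | Full-exposure ratio | Understated by |
|---|---|---|---|---|---|
| 1 | 11 | 3 | 1.95 | 2.27 | 14% |
| 3 | 11 | 3 | 1.85 | 2.80 | 34% |
| 1 | 11 | 1 | 1.89 | 2.00 | 5% |
| 3 | 11 | 1 | 1.68 | 2.00 | 16% |
| 1 | 44 | 1 | 1.98 | 2.00 | 1.0% |
| 1 | 44 | 3 | 2.21 | 2.27 | 2.7% |
| 3 | 44 | 1 | 1.94 | 2.00 | 3.1% |
| 3 | 44 | 3 | 2.62 | 2.80 | 6.6% |

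**Power.** Simulation with 8000 runs: Poisson counts with gamma frailty (shape 2), placebo mean 10 events per 52 weeks, Kruskal-Wallis at 0.05, exposure in weeks.

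| Scenario (rate ratio 2 unless stated) | Counts | Rates |
|---|---|---|
| No stops | 0.59 | 0.59 |
| 1 stop, week 11, m = 3 | 0.56 | 0.65 |
| 3 stops, week 11, m = 3 | 0.47 | 0.75 |
| 3 stops, week 11, m = 3, 70% of events in weeks 0–22 | 0.60 | 0.78 |
| 3 stops, week 44, m = 1 | 0.55 | 0.59 |
| 1 stop, week 11, m = 1 | 0.45 | 0.58 |
| 3 stops, week 11, m = 1 | 0.20 | 0.56 |
| 3 stops, week 11, m = 1, rate ratio 5 | 0.97 | 1.00 |

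With no true rate difference, three week-11 stoppers at m = 1 make the count test reject about 9% of the time, against 5% on rates.

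**Does a plain rate cure it?** Not fully. Suppose 70% of events fall in weeks 0–22 and three children stop at week 11. Each stopper contributes 0.70·11/22 = 35% of a year's events in 11 weeks.

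- m = 1 (full-exposure ratio 2.00): counts give 2·(12 + 3·0.35)/15 = 1.74; the pooled rate gives 2·13.05·52/657 = 2.07, where 657 = 12·52 + 3·11; the mean of child rates gives 2·(12 + 3·0.35·52/11)/15 = 2.26.
- m = 3 (full-exposure ratio 2.80): counts give 2·(12 + 9·0.35)/15 = 2.02; the mean of child rates gives 2·(12 + 9·0.35·52/11)/15 = 3.59.

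Early stoppers pull an unstratified rate towards build-up, so phase has to be in the analysis.

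**The case against.** **Counts answer a legitimate question.** Events per randomised child in year 1 measure the burden of being assigned to OIT, and stopping does prevent later reactions. The understatement exists only against a target of event rate while on treatment. The plan's phrase about events on OIT leans that way but does not settle it. This stands, and it is why the count comparison should be kept.

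**The lowest power figures rest on an unlikely case.** The 0.45 and 0.20 assume m = 1: children who stop because they react, yet react no more than completers. A reader might infer that the primary test is likely to fail. The documents do not support that. They give no event rate, rate ratio or stop week, and at m = 3 with one stopper the count test loses little (0.56 against 0.59 with no stops).

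**The earlier baked-milk study is not a forecast.** Section 3 reports eight of 14 or 15 patients stopping for IgE-mediated reactions, and a reader might carry that rate over. The protocol starts at a far lower dose and escalates more slowly because of that result.

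**The benchmark is not only per dose.** Sections 3 and 8.a.i also cite a per-child figure: 47% with moderate reactions in a 1-year study of 2–3-year-olds. The plan contains no formal comparison with historical rates, so the benchmark point is secondary.

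**Rates have their own faults.** A child with few doses has an unstable rate, and an unstratified rate can overshoot, as shown above. A negative binomial Wald test at 15 per arm, with no stopping and no true difference, rejected 9% of the time in 600 runs. This stands and shapes the fix.

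**Partial cover exists.** Serious events already have a per-dose comparison, so the gap concerns all other adverse events.

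**Conclusion.** The point holds, at moderate weight. Section 7.c tests all adverse events on raw counts alone, and the protocol's rules end dosing and most event capture early for children who react. If those children are mainly on active treatment, counts tend to understate the event rate on OIT. The direction depends on that inference; the size depends on assumed inputs. With stoppers reacting at three times the completers' rate and stopping at week 11, the ratio is 14% too low for one stopper and 34% too low for three. With stops near week 44 it is 1.0% to 6.6% too low. Power loss is also small if the true ratio is large.

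It would go too far to say that the count analysis is invalid or that the trial will miss a real excess. Neither follows from the documents.

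**What to change.** Keep the per-child count comparison in Section 7.c, labelled as the burden of assignment, and add this as the main comparison:

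> We will compare adverse events per dose taken, from escalation day to DBPCFC #2, between groups in all randomised children who were dosed, stratified by phase (escalation, build-up, maintenance), using a rank or permutation test on each child's rate. We will estimate the rate ratio with log(doses taken) as offset and phase as a term, with permutation or small-sample inference. We will report the number, reason and study week of discontinuations by arm.

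The cost is a few sentences. The daily diary (Section 4.D) already records dosing and adverse events, and the planned test of serious events already needs dose counts, so no new data, visits or children are required.

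Two downsides remain. Rates from children with few doses are unstable. Maintenance-phase rates come only from children who got through build-up, so they should be read beside the discontinuation table. The simulations used weeks as exposure and did not test the phase-stratified analysis, so its behaviour at 15 per arm should be checked before the text is fixed.
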